7.7 Inclusion and Exclusion criteria

- **Inclusion Criteria:**

1. Patients diagnosed with ACS, including ST-Elevation Myocardial Infarction (STEMI), Non-ST-Elevation Myocardial Infarction (NSTEMI), or Unstable Angina within the last 12 months.
2. Patients aged 18 years and older.
3. Patients willing to participate and provide informed consent for the study.

- **Exclusion Criteria:**

1. Individuals who have not been diagnosed with ACS or those with other acute or chronic conditions that might influence medication adherence unrelated to ACS.
2. Patients with cognitive impairments or mental health issues that prevent them from understanding or responding accurately to the study questionnaires.
3. Patients with severe chronic conditions (e.g., terminal illness, advanced dementia) that may affect their ability to adhere to medication regimens.

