In summary, this study is essential for understanding why patients in Nepal fail to adhere to life-saving medications post-ACS and what can be done to mitigate this problem, ultimately improving patient care and reducing the burden on the healthcare system.

5. Objectives

a. General objectives:

To assess the level of adherence to prescribed secondary prevention medications and identify the factors influencing adherence among patients with Acute Coronary Syndrome (ACS) in Nepal.

b. Specific objectives:

- **To assess the level of adherence to secondary prevention medications (SPMs) among patients discharged after an Acute Coronary Syndrome (ACS) event, including antiplatelets, statins, beta-blockers, and ACE inhibitors/ARBs.**
- **To explore the influence of patient demographic factors** (such as age, gender, education level, occupation, and place of residence) and clinical characteristics (type of ACS, comorbidities) on medication adherence.
- **To identify patient-reported barriers to medication adherence**, including concerns about medication side effects, pill burden, practical issues with medication administration, and difficulties in integrating medications into daily routines.
- **To evaluate the relationship between medication adherence and clinical outcomes**, such as recurrent cardiac events, rehospitalization.

6. Research questions/hypothesis

- What is the level of adherence to secondary prevention medications among Acute Coronary Syndrome (ACS) patients in Nepal, and what demographic, clinical, and patient-reported factors influence this adherence and its associated clinical outcomes?

7. Research design and Methodology

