7.3 Study population/Sampling frame

A sample of adult patients (age ≥ 18 years) who have either come to OPD for follow-up or have been readmitted for having cardiac complications months after surviving ACS (including STEMI, NSTEMI, and unstable angina) in Manmohan Cardiothoracic Vascular and Transplant Centre, Nepal will be selected via **convenience sampling**. The total population under study is around 1000.

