7.4 Study site and its justification

This descriptive cross-sectional study will be conducted at Manmohan Cardiothoracic Vascular and Transplant Centre, a premier tertiary care institution in Nepal, specializing in cardiovascular care. As one of the nation's leading centres for heart disease management, it offers advanced diagnostic, therapeutic, and surgical services to patients with a wide spectrum of cardiovascular conditions, including Acute Coronary Syndrome (ACS). The centre's reputation for excellence in cardiology and its strategic location make it an ideal setting for research into adherence to secondary prevention medications after ACS.

The patient population at this centre is diverse, including individuals from both urban and rural areas of Nepal, which provides a comprehensive understanding of medication adherence patterns across various demographic and socioeconomic groups. The centre regularly follows up with ACS survivors, both through outpatient visits and during readmissions for cardiac complications. This makes it a prime location to study patients who have either come for follow-up visits or been readmitted within 12 months of their initial ACS event, including STEMI, NSTEMI, and unstable angina.

By focusing on this centre, the research will leverage the expertise of its specialized staff and access to detailed patient records, providing valuable insights into medication adherence in real-world clinical practice. These insights can then be used to inform targeted interventions to improve long-term outcomes for ACS survivors across Nepal.

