7.5 Sampling method

In our research study, we will employ convenience sampling. Convenience sampling is a non-probability method where units are selected for inclusion in the sample because they are the easiest for the researcher to access. The target population consists of adult patients (age ≥ 18 years) who have either come to OPD for follow-up or have been readmitted in hospital for having cardiac complications months after surviving ACS (including STEMI, NSTEMI, and unstable angina). Rather than applying specific

stratification based on cancer type, we will approach patients who are readily available within the hospital setting. We will use the MYMEDS questionnaire. The researcher will personally ask all the questions and fill out the questionnaire for each eligible patient. To assess the socioeconomic status of participants, we will utilize the Modified Kuppuswamy's Socioeconomic Status Scale, adapted to the context of Nepal (18). Alongside demographic information such as gender, age at diagnosis, and marital status, we will collect data on education level, occupation, and family income, as per the scale's criteria(18).

Once we collect the responses, we will use MS Excel for data entry and analyze the data using SPSS version 29.

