7.10 Tools and techniques for data collection

- Tools:

Questionnaire

The questionnaire is composed of six simple-to-complete sections.

Section 1:

- Patients provide essential contextual information about the medicines they are taking, when they are administered each day, and their understanding of why they are taking them.
- This helps clinicians compare a patient's actual medication usage with documented clinical records and uncover any medication changes since discharge.

Subsequent sections (Section 2-6):

- These sections use Likert scales instead of binary yes/no responses, which improves the quality of information gathered.
- For example, it allows the assessment of the frequency of non-adherence behaviors rather than just detecting non-adherence.

Section 2:

- Explores overall understanding and satisfaction with medicines.
- Patients respond to four statements regarding their understanding of why their medicines were prescribed and how well they think they are working, using a four-point Likert scale (strongly agree, agree, disagree, strongly disagree).

Sections 3–5:

- Assess specific modifiable barriers to adherence, using the same four-point Likert scale as section 2.
- A free-text box allows patients to specify which medicines their concerns involve.

Section 3:

- Explores three areas of anxiety about medicines (e.g., concerns about medicines causing more harm than good or feeling there are too many medicines).

Section 4:

- Examines four practical concerns associated with medicine-taking (e.g., difficulties with swallowing pills or obtaining repeat prescriptions).

Section 5:

- Assesses three issues related to fitting medicines into the patient's daily routine (e.g., forgetfulness or inconvenience).
- These issues are linked to non-adherence and can potentially be addressed in clinical practice.

Section 6:

- Focuses on adherence to each individual secondary prevention medication (SPM) over the past month.
- It uses a modified version of the SQ tool and a five-point Likert scale.
- Patients are considered non-adherent if they select any answer other than 'all of the time' for any SPM.

[figure not shown]
Technique:

- A relevant questionnaire will be developed and distributed to our research team. They will visit cardiology outpatient department (OPD) as well as in the cardiology ward in Manmohan

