	c. I have difficulties or problems getting my repeat prescriptions and would like help ordering them from my GP or pharmacy.				
	d. I have difficulties or problems reading the label on the medicines bottle or box and would like a solution or alternative.				

Section 5: Fitting medicines into daily routine	a. I sometimes forget to take my heart medicines.				
	b. I am finding it difficult to fit one or more of my heart medicines into my daily routine.				
	c. I feel inconvenienced/bothered about sticking to all my heart medicines.				

Section 6: Adherence to Individual SPMs

For each of your prescribed medicines (SPMs), please indicate how often you have taken them as prescribed in the PAST MONTH:

Medication	All of the Time	Nearly All of the Time	Most of the Time	About Half the Time	Less than Half the Time
Aspirin					
ACE Inhibitor (e.g. Ramipril, Lisinopril,)					
Beta Blocker (e.g. Acebutalol)					
Medication 4 Statin (e.g. Simvastatin)					
ARIIA (e.g. Candesartan)					

Section 4: Clinical Outcomes

1. **Have you experienced any of the following since discharge?** (Check all that apply)
 - Recurrent chest pain
 - Rehospitalization for cardiac issues
 - Stroke
 - Heart failure symptoms
 - No major events
2. **Follow-up with healthcare provider since discharge:**
 - Yes
 - No
 - If Yes, how many visits: _____

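### Readmitted patients answer a past-month adherence question on the ward, so the recall window includes the current admission, and the form lacks the dates to separate those days

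*Combined protocol and SAP*

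**What the plan says.** **Recall period.** Section 7.10 describes the adherence part of the questionnaire: "Focuses on adherence to each individual secondary prevention medication (SPM) over the past month". The annexed form repeats this ("please indicate how often you have taken them as prescribed in the PAST MONTH") and gives no instruction about days spent in hospital. Under 7.10, a patient who chooses anything below the top frequency category for any secondary prevention medicine is classed as non-adherent.

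**Who is interviewed, and where.** Sections 7.3 and 7.5 describe two groups: patients attending the OPD for follow-up, and patients who "have been readmitted for having cardiac complications months after surviving ACS". The technique part of 7.10 sends the team to both the cardiology OPD and the cardiology ward.

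**Timing.** Inclusion criterion 1 in 7.7 requires ACS ("or Unstable Angina within the last 12 months"). Section 7.4 likewise gives only an upper limit ("been readmitted within 12 months of their initial ACS event"). The phrase "months after surviving ACS" in 7.3 and 7.5 implies some delay but gives no number and is not carried into 7.7.

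**Target.** The first specific objective concerns adherence "among patients discharged after an Acute Coronary Syndrome (ACS) event". The fourth relates adherence to recurrent events and rehospitalisation.

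**Dates.** The pro forma records the date of ACS diagnosis. It has no field for index discharge, readmission, interview date or interview setting.

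**The concern.** The study wants to know how patients take their medicines after discharge. A patient interviewed some days into a readmission is asked about a period that is partly spent in hospital, where missing a dose is probably much harder. Under an all-or-nothing rule, every day removed from risk raises the chance of being classed as adherent.

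The overlap is not spread evenly. It falls on patients interviewed as inpatients, and all of them are rehospitalised. Adherence is therefore measured over fewer at-risk days in the group that defines one of the outcomes in the fourth objective. If non-adherence does lead to readmission, this pulls the observed association towards no effect. It also distorts the OPD-versus-ward contrast, which section 9 already treats as delicate for other reasons. Section 9 lists selection, survivor and self-report bias, but not this one.

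An OPD patient seen within a month of discharge has a related difficulty. Part of the past month is the index stay, and part may precede the ACS, when the medicines may not yet have been prescribed.

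**Working it through.** **The plan's own figure, as a yardstick.** Section 7.6 gives p = 0.925, d = 0.05 and z = 1.96. Then n = 1.96² × 0.925 × 0.075 / 0.05² = 106.6. The plan states 106.39 and uses 106; 106 × 1.10 = 116.6, so 117. The sample size reproduces, and this point does not change it. The useful figure is the 5-point margin of error.

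**Assumptions not in the documents.** The protocol gives no ward share, length of stay or visit timing. I take a 30-day window, k ward days within it, a constant and independent daily chance of a miss, and no misses on ward days. If p is the chance of no miss in 30 days at home, the chance with k ward days is p^((30 − k)/30). The result is the same whether patients count ward days as taken or ignore them. It would not apply if they answered only about their habits before admission.

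**Share of the window spent on the ward.** For k = 1, 3, 5, 7 and 10, k/30 = 3%, 10%, 17%, 23% and 33%.

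**Effect with k = 7, true adherence equal in both groups, 30% of the sample affected.** Overall = 0.7 × p + 0.3 × p^(23/30).

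| p at home | Apparent, ward group | Gap (points) | Odds ratio, ward vs OPD | Overall | Rise (points) |
|---|---|---|---|---|---|
| 0.925 | 0.942 | 1.7 | 1.32 | 0.930 | 0.5 |
| 0.70 | 0.761 | 6.1 | 1.36 | 0.718 | 1.8 |
| 0.50 | 0.588 | 8.8 | 1.43 | 0.526 | 2.6 |

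The odds ratio is [a/(1 − a)] / [p/(1 − p)], where a is the apparent adherence in the ward group. For example, at p = 0.70 it is (0.761/0.239) / (0.70/0.30) = 1.36. It would be 1.00 without the overlap.

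**Sensitivity of the overall rise** (at p = 0.925, 0.70 and 0.50):
- Ward share 10%, k = 7: 0.2, 0.6 and 0.9 points.
- Ward share 50%, k = 7: 0.8, 3.0 and 4.4 points.
- Ward share 30%, k = 3: 0.2, 0.8 and 1.1 points.
- Ward share 30%, k = 10: 0.7, 2.7 and 3.9 points.

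**Early OPD patients.** If interviews fell evenly over the 12 months, about 30/360 = 8.3% of patients would be within 30 days of discharge, or about 10 of 117. A patient seen 14 days after a 5-day stay has 14 days at home, 5 in hospital and 30 − 14 − 5 = 11 before the ACS. If only the 14 home days carry risk, apparent adherence is p^(14/30) = 0.964, 0.847 and 0.724. The overall rise is 0.083 × (0.039, 0.147, 0.224), or about 0.3, 1.2 and 1.9 points. The direction is less certain here, because it is unknown how patients would answer for days before the medicines were prescribed.

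**The case against.** **Index inpatients.** Reading 7.7 alone, one might infer that a patient still in the index admission is eligible. The documents do not support that. Sections 7.3 and 7.5 limit the population to OPD attenders and readmitted patients, and the first specific objective concerns discharged patients.

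**The delay wording.** The phrase "months after surviving ACS" covers readmitted patients on any reading and may be meant for OPD patients too. It largely keeps the index stay out of a ward patient's recall window. It does nothing about the current stay, and it leaves the OPD group without a clear lower limit.

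**Size.** One might infer that these patients look adherent by design, or that the headline estimate is badly inflated. Neither follows. A patient who reports a miss on any of the remaining home days is still classed as non-adherent, and every overall rise computed here is below the plan's 5-point margin. Supervised inpatient dosing is itself an inference. This part of the objection stands. The margin, however, describes sampling error, whereas this shift is systematic and falls on one group.

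**Early patients belong to the target.** Good adherence in the first weeks at home is real adherence. A one-month minimum as an entry criterion would change the population and would also drop early readmissions. This stands, and is why no exclusion is proposed.

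**Records.** Section 7.9 plans medical record review, so dates might be recovered. That helps only if someone is told to collect them, and the pro forma gives no place to write them.

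**Conclusion.** The point holds for readmitted patients. As written, their past-month answers include days of the current admission, and the form cannot identify which days. The effect on the overall adherence estimate is modest: about 0.5 points at 92.5% and 1.8 to 2.6 points at 70% to 50%, with 7 ward days and 30% of the sample affected. The comparison between groups suffers more. Equal true adherence would appear as a gap of 1.7 to 8.8 points, with an odds ratio of about 1.3 to 1.4 in favour of ward patients. The adherence-rehospitalisation result would be affected less if some OPD patients had also been rehospitalised earlier.

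The missing minimum time since discharge is a secondary matter that mainly concerns early OPD visits. All sizes rest on the assumed ward share, ward days, visit timing and independent daily misses. The structural finding rests only on the recall wording, the ward interviews and the missing dates.

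**What to change.** 1. In MYMEDS Section 6, ask readmitted patients about the month before the current admission.
2. Ask patients discharged less than a month ago about the days since discharge. Apply the same starting point to anyone readmitted within a month of index discharge.
3. Add index discharge date, current readmission date (if any) and interview date to the pro forma.
4. Report a sensitivity analysis that excludes patients with less than one month at home. It is needed because step 2 removes hospital and pre-ACS days but still leaves those patients with fewer days at risk.

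The cost is one or two lines of interviewer wording, three date fields and one extra analysis. Eligibility and the target of 117 do not change. The downside is a small departure from the standard questionnaire wording and recall periods that differ slightly between groups. Both should be stated in the report.

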7.8 Study variables

Dependent Variable:

- **Adherence to Secondary Prevention Medications (SPMs):** This includes adherence levels to specific medications such as antiplatelets, statins, beta-blockers, and ACE inhibitors/ARBs, measured through MYMEDS questionnaire.

Independent Variables:

1. Demographic Factors:

- Age
- Gender
- Education Level
- Occupation
- Place of Residence (Rural vs. Urban)
- Monthly Income

2. Clinical Characteristics:

- Type of Acute Coronary Syndrome (e.g., STEMI, NSTEMI, Unstable Angina)
- Comorbidities (e.g., Hypertension, Diabetes Mellitus, Dyslipidemia, Chronic Kidney Disease)

3. Patient-Reported Factors:

- Concerns about medication side effects
- Pill burden (number of medications)
- Practical issues with medication administration (e.g., difficulties opening bottles)
- Difficulty integrating medications into daily routines

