7.1. Research method

Quantitative Survey: The adherence to secondary prevention medications among re-hospitalized patients after cardiac complications following Acute Coronary Syndrome (ACS) will be evaluated using a structured questionnaire. This survey will assess patient demographics, socioeconomic status, and barriers to adherence such as medication cost, side effects, and treatment complexity. Administered either in person or via an online platform, the survey will collect key data on adherence patterns and influencing factors in high-risk patients. This method aims to ensure efficient data collection while maintaining confidentiality and ease of access for participants.

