 - 4. Semi-skilled worker**
 - Factory or workshop laborer, laboratory or library attendant, car cleaner

5. Unskilled worker

- Watchman, peon, domestic servant, rickshaw puller

6. Unemployed

9. **Family Monthly Income (NPR):** _____

- $\geq 97,451$
- 48,751–97,450
- 36,551–48,750
- 24,351–36,550
- 14,551–24,350
- 4,851–14,550
- $\leq 4,850$

10. **Place of Residence:**

- [] Rural
- [] Urban

11. **Distance from Healthcare Facility:** _____ (km)

Section 2: Clinical Information

1. **Type of ACS:**

- [] ST-Elevation Myocardial Infarction (STEMI)
- [] Non-ST-Elevation Myocardial Infarction (NSTEMI)
- [] Unstable Angina

2. **Date of ACS Diagnosis:** _____

3. **Treatment Received:**

- [] Percutaneous Coronary Intervention (PCI)
- [] Coronary Artery Bypass Grafting (CABG)
- [] Medical Management Only

4. **Comorbidities:**

- [] Hypertension
- [] Diabetes Mellitus
- [] Dyslipidemia
- [] Chronic Kidney Disease
- [] Stroke
- [] Peripheral Arterial Disease
- [] Others (Specify): _____

Section 3: Assessment of Adherence**MYMEDS Questionnaire****Section 1: Current Medicines**

Serial Number	Name of Medicines	Administration Time (Morning/Afternoon/Evening/Night)	Reason for Taking Medicine
1	Antiplatelets	_____	_____
2	Statins	_____	_____
3	Beta-blockers	_____	_____
4	ACE inhibitors/ARBs	_____	_____
5	Others (Loop diuretics, Nitrates, specify)	_____	_____

Section Number	Statement	Strongly agree	Agree	Disagree	Strongly disagree
Section 2: Understanding and satisfaction with medicines	a. I fully understand my heart medicines and why they were prescribed.				
	b. My heart medicines seem to be working for me.				
	c. I feel convinced of the importance of all my heart medicines.				
	d. At least occasionally, I need to alter my medicines on my own to make them work or meet my expectations.				

Section 3: Concerns about medicines	a. I worry that one or more of my medicines will do me more harm than good.				
	b. I feel concerned about being prescribed too many medicines.				
	c. I sometimes alter my medicines by cutting back or stopping taking them. (e.g. due to feeling worse, getting worried or for any other reason)				
Section 4: Practical issues that may be a barrier to adherence	a. I have difficulties or problems opening the medicine bottles or blister packs and would like a solution or an alternative.				
	b. I have difficulties or problems swallowing my medicine(s) and would like a solution or an alternative.				

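### Side effects are a barrier the survey says it will assess, but the form reaches concern about them only through broad proxy items and never asks whether one occurred

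*Combined protocol and SAP*

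**What the plan says.** Side effects appear in three places in the plan.

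- Section 5b, third specific objective: the barriers to be identified are introduced as "including concerns about medication side effects, pill burden" and then practical and routine-related difficulties.
- Section 7.8, patient-reported factors: the first entry is "Concerns about medication side effects".
- Section 7.1: the structured questionnaire is to assess "barriers to adherence such as medication cost, side effects, and treatment complexity". Here the barrier is side effects, not concern about them.

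The instrument is MYMEDS, reproduced in Annex 1. Section 7.10 describes its Section 3 as covering three areas of anxiety, with the examples "concerns about medicines causing more harm than good or feeling there are too many medicines". It also says of Sections 3 to 5: "A free-text box allows patients to specify which medicines their concerns involve". On the annexed form, item 3a reads "I worry that one or more of my medicines will do me more harm than good". Item 3c asks about cutting back or stopping medicines and offers feeling worse as one example reason among others. Section 8, where variable definitions and analysis methods would be expected, holds only the template prompts.

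**The concern.** A factor named in an objective and listed as an independent variable should have an identifiable item behind it. Here the first-named barrier has none that mentions it. The analyst will have to choose between items 3a and 3c, or combine them, after the data are in. The two items measure different things, and neither is specific to side effects.

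At stake is what the report can say under objective 3. A result from 3a describes patients who doubt that their medicines do them net good. That may include fear of side effects, but also general distrust or doubt about benefit. If it is presented as side-effect concern without qualification, readers cannot tell these apart, and section 13 says the findings will inform targeted interventions. For the 7.1 barrier, side effects experienced, there would be nothing to report.

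**Working it through.** The plan states no figure on this point, so the check compares the promised factors with the items on the annexed form.

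**Step 1. Count the statements.** MYMEDS Sections 2, 3, 4 and 5 on the form hold 4 + 3 + 4 + 3 = 14 agree/disagree statements. Statements naming side effects: 0 of 14.

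**Step 2. Look elsewhere on the form.** MYMEDS Section 1 records the medicine, the time taken and the reason. MYMEDS Section 6 records how often each medicine was taken in the past month. The clinical outcomes question offers five options: recurrent chest pain, cardiac rehospitalisation, stroke, heart failure symptoms and no major events. Fields asking whether a side effect occurred: 0.

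**Step 3. Match each patient-reported factor in 7.8 to its items.**

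| Factor in 7.8 | Items on the form | Match |
|---|---|---|
| Side-effect concern | 3a; 3c in part | Indirect |
| Pill burden | 3b, and the medicines list | Direct |
| Practical issues | 4a to 4d | Direct |
| Daily routine | 5a to 5c | Direct |

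Side effects are the only one of the four factors without a direct item.

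**Step 4. Ask what the two nearest items measure.**

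- *Item 3a* is a net judgement. A patient who worries about side effects but believes the medicine is worth taking can truthfully disagree. A patient with general distrust and no particular worry about side effects can truthfully agree. So 3a can be wrong in both directions as a measure of side-effect concern. The documents give nothing from which to estimate how often.
- *Item 3c* joins several reasons in one statement, so the share due to feeling worse cannot be recovered. It also asks about reducing or stopping medicines, which is non-adherence. As a predictor of adherence it would partly correlate the outcome with itself.

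**Step 5. Check the other possible sources.** The free-text box described in 7.10 identifies the medicine involved, not the nature of the concern. Section 11 says adverse events will be recorded, but that sentence is about the safety of taking part, and the form has no field for it.

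**Step 6. Look for a definition.** No section states that 3a, 3c or a combination defines the 7.8 variable.

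**The case against.** The strongest reply is that the variable in 7.8 and objective 3 is a concern, not an occurrence, and that the form has a block on concerns whose first item is about harm from medicines. The 7.8 list also follows the order of the instrument: concern (3a), pill burden (3b), practical issues (Section 4), routine (Section 5). On that reading 3a is evidently the intended measure. A patient who has side effects but is not worried by them should answer no to a concern item. All of this is fair, and it means the concern factor is not uncollected.

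Two further points carry weight. The reference to side effects in 7.1 is part of an illustrative list in a general paragraph, not an objective or a listed variable. And MYMEDS was chosen as an existing questionnaire for patients after myocardial infarction, so any added items would be untested.

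What the reply does not remove is that 3a is broader than side effects, that the link from 3a to the variable has to be inferred, and that 7.1 still says the survey will assess a barrier for which the form has no field. The pro forma already surrounds MYMEDS with other sections, so items placed outside the block would leave the instrument intact.

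**Conclusion.** The point holds as a gap between what is promised and what is measured. Concern about side effects can be reported only through a broad proxy that the plan does not assign. Experienced side effects cannot be reported. The extent is 0 of 14 statements naming side effects and 0 fields on occurrence. This is worth correcting because it affects the first-named barrier of a stated objective and the remedy is small.

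A reader might go further and infer that the side-effect factor cannot be reported at all. The documents do not support that, because item 3a does capture worry about harm. A reader might also infer that 3a will be presented as side-effect concern and that interventions will then be misdirected. No section says 3a will be relabelled, so that is a risk, not a stated plan. Nor can a number of affected patients be given: the documents state no side-effect rate, and a rate of occurrence would not show how often 3a misclassifies concern.

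The conclusion assumes that the annexed form is the one to be used. A figure in section 7.10 is not shown in the available text, and the same section speaks of a questionnaire still to be developed.

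**What to change.** **If the form can still be changed,** add two short items outside the MYMEDS block:

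1. Side effects from any heart medicine since discharge: yes or no, and which medicine.
2. Worry about side effects of the heart medicines, on the four-point agreement scale already used in Sections 2 to 5.

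Use item 2 as the 7.8 variable and item 1 for the barrier named in 7.1. Report both apart from MYMEDS and describe them as untested. Report 3a under its own label, benefit-harm worry. Do not use 3c as a predictor of adherence. Write these definitions into section 8.

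The cost is two questions, a slightly longer interview, and two results that lack the support of an existing instrument.

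**If the form can no longer be changed,** define the variable as item 3a, reword objective 3 and 7.8 to *concern about harm from medicines*, and remove side effects from the barriers that 7.1 says will be assessed. This needs only text edits, but the study then gives up any statement about side effects specifically.
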